4.3.7 MRI of hip(s)

Information on hip(s) MRI (STIR (short tau inversion recovery) sequence and fat-saturated contrast-enhanced T1-weighted sequence) will be collected for patients based on availability. If MRI done at screening, information on MRI is not required at baseline.

Information on hip(s) MRI (STIR (short tau inversion recovery) sequence and fat-saturated contrast-enhanced T1-weighted sequence) will be collected for patients based on availability in the patient charts at 6, 12 months to evaluate changes of inflammation parameters.

The following parameters of active inflammation will be determined:

- No lesions suggesting inflammation
- Subchondral bone marrow edema (expressed as Yes or No)
- Joint effusion (expressed as Yes or No)
- Enthesitis at sites where ligaments and tendons are attached to bone in structures adjacent to the hip joint (expressed as Yes or No)
- Fatty degeneration (expressed as Yes or No)
- Change of a parameter from previous examination (Positive change or No change or Negative change)

At the moment, there is no standardized MRI scores available for hips. This is the reason for collecting information on each individual MRI sign of inflammation and for placing change of MRI signs in the Exploratory objectives.

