MRI can detect soft tissue and bone inflammation of hip. There was a recent Chinese study investigating inflammatory MRI changes in AS patients investigating pattern of hip involvement. Active inflammatory changes included subchondral bone marrow edema, joint effusion, abnormal synovial enhancement, enthesitis at sites where ligaments and tendons are attached to bone. They are visualized

Product: MK-8259

Protocol/Amendment No.: 021

VEAP ID NO: 6189

Date: 15-January-2018

best by STIR (short tau inversion recovery) sequence and fat-saturated contrast-enhanced T1-weighted sequence. Chronic inflammatory changes were fatty degeneration, erosive destruction, joint space narrowing, sclerosis, ankylosis. They are best seen by using a T1-weighted TSE sequence [10]. The proportion of hip involvement according to MR imaging, radiographs, and clinical symptoms was:

	Proportion of hip involvement
MRI	74,1% (86/116)
Radiography	20,7% (24/116)
Clinical symptoms	30,2% (35/116)

MRI yielded higher values than radiographs and clinical symptoms in the detection of hip involvement in patients with AS ($P <0.05$). The frequency of MRI changes in 81 hips (42 patients) have been shown to be: acute changes alone – 43,1%, chronic and acute changes – 26,7%, normal – 25,9%, chronic changes – 4,3%. The rates of acute MRI inflammatory changes have been shown to be:

	Rates of acute MRI inflammatory changes
Synovitis alone	48,1%
Synovitis + bone edema	21,0%
Synovitis + bone edema + enthesitis	18,5%
Synovitis + enthesitis	8,6%
Bone edema alone	3,7%
Enthesitis alone	0
Bone edema and enthesitis	0

There are no studies investigating correlation of different radiological manifestations over time.

According to current international guidelines, management of AS patients with coxitis does not differ from management of AS patients without hip involvement and includes physiotherapy, pharmacological therapy (NSAIDs, sulfasalazine, TNF alpha inhibitors) and surgery [8,11,12,13]. The latter is total hip replacement which is used in cases of end-stage disease [9]. In analysis of three databases of AS patients (Belgian database ASPECT, n=847, Spanish database REGISPOSNER, n=1405 and Ibero-American database RESPONDIA, n=466), it was shown that 5-8% of the AS patients undergo hip replacement surgery, 47% of them have bilateral hip replacement. After >30 years of disease duration, the chance of having at least one replaced hip is 12-25% [4]. Investigators who were analyzing Norwegian

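### The MRI list in section 4.3.7 has no synovitis item and labels fatty degeneration as active, against the protocol's own Background (minor; exploratory analyses only)

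*Combined protocol and SAP*

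**What the plan says.** Section 4.3.7 states "Information on hip(s) MRI (STIR (short tau inversion recovery) sequence and fat-saturated contrast-enhanced T1-weighted sequence) will be collected for patients based on availability". It then opens the item list with "The following parameters of active inflammation will be determined". The items are: no inflammatory lesions, subchondral bone marrow edema, joint effusion, enthesitis, "Fatty degeneration (expressed as Yes or No", and change of a parameter since the previous examination. The section explains that each sign is collected individually because no standardized hip MRI score exists.

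The Background (section 1.1) draws the line between active and chronic change: "Active inflammatory changes included subchondral bone marrow edema, joint effusion, abnormal synovial enhancement, enthesitis at sites where ligaments and tendons are attached to bone". These are visualized "best by STIR (short tau inversion recovery) sequence and fat-saturated contrast-enhanced T1-weighted sequence". For the chronic group it says "Chronic inflammatory changes were fatty degeneration, erosive destruction, joint space narrowing, sclerosis, ankylosis", and "They are best seen by using a T1-weighted TSE sequence". Section 1.2 ranks synovitis and its combinations with edema and enthesitis as the most frequent MRI findings, and adds that nothing is known about how these findings change over time.

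Change in MRI signs, and clinical scores in subgroups with or without MRI/US signs at baseline, are exploratory (sections 2.3 and 8.1.4). Change in MRI signs is to be reported descriptively.

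**The concern.** The list leaves out one of the four active signs that the Background names, and it is the one that the Rationale puts first. It also includes one sign that the Background places in the chronic group.

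The CRF is still to be developed from the protocol (section 6.1.2.2), and section 6.1.2.4 does not say which signs the central reading records. If both follow section 4.3.7, the study will have no named record of synovitis for its exploratory objective on change in MRI signs, even though the lack of such data is part of the study's stated justification.

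**Working it through.** **1. The two lists side by side**

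| Sign | Section 1.1 | Section 4.3.7 list |
|---|---|---|
| Bone marrow edema | active | listed |
| Joint effusion | active | listed |
| Abnormal synovial enhancement | active | not listed |
| Enthesitis | active | listed |
| Fatty degeneration | chronic | listed under active inflammation |

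Section 4.3.7 names both sequences that section 1.1 says show active change best, including the contrast-enhanced one, but has no item for enhancement. It does not name the T1-weighted TSE sequence that section 1.1 links to chronic change.

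**2. Is the item supplied elsewhere?** No. Sections 3.1, 4.3 and 6.1.3.10 and the flow chart mention only MRI, its sequences or MRI signs in general. The ultrasound list in section 4.3.8 has effusion, a distance from femoral neck to joint capsule, and enthesitis. It has no item for synovial hypertrophy or vascularity, although section 1.1 says ultrasound can show both.

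**3. Denominator of the acute-change table.** Section 1.1 introduces the overall breakdown with "The frequency of MRI changes in 81 hips (42 patients) have been shown to be", but that breakdown includes normal hips. Its percentages fit 116, the denominator of the hip-involvement table:

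- 50/116 = 43.1% (acute only), 31/116 = 26.7% (acute and chronic), 30/116 = 25.9% (normal), 5/116 = 4.3% (chronic only).
- 50 + 31 + 30 + 5 = 116, and 50 + 31 + 5 = 86, the stated number with MRI involvement.
- With 81 as denominator, 43.1% cannot be obtained: 35/81 = 43.2% and 34/81 = 42.0%.

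Acute change with or without chronic change is then 50 + 31 = 81. So the 81 hips are taken to be those with acute change. This is an inference; the document does not say it.

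**4. Counts in the acute-change table (of 81)**

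| Category | Stated % | Hips |
|---|---|---|
| Synovitis alone | 48.1 | 39 |
| Synovitis + edema | 21.0 | 17 |
| Synovitis + edema + enthesitis | 18.5 | 15 |
| Synovitis + enthesitis | 8.6 | 7 |
| Edema alone | 3.7 | 3 |
| Enthesitis alone; edema + enthesitis | 0 | 0 |

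The counts sum to 81. Any synovitis: 39 + 17 + 15 + 7 = 78, and 78/81 = 96.3%. Synovitis as the only tabulated sign: 39/81 = 48.1%.

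**5. Share of acutely changed hips with no listed active sign.** The table has no row for effusion. Let p be the share of synovitis-only hips that also have effusion, which the documents do not give. The share with no listed active sign is 48.1% × (1 − p):

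| p (assumed) | 0 | 0.25 | 0.5 | 0.75 | 1 |
|---|---|---|---|---|---|
| Share | 48.1% | 36.1% | 24.1% | 12.0% | 0% |

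The documents support only the full range, 0 to 48.1%. They give no rate for fatty degeneration, so no figure is attached to that half.

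**The case against.** The strongest reply is that little may be lost.

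- **Effusion may stand in for synovitis.** Section 1.1 describes a 12-month etanercept cohort whose MRI result was reported as fluid synovitis of the hip joint, and synovitis in the acute-change table may include effusion. This stands in part, and it is why the range reaches 0. It does not close the gap, because section 1.1 lists effusion and synovial enhancement as separate active signs and gives no overlap.
- **The list has an item for no inflammatory lesions.** A hip with synovitis alone should not be given that entry, so it can still be told apart from a normal hip, and its resolution could appear as a switch to that item. This stands. What is lost is the named sign, not the detection of inflammation. A reader might infer that up to half of inflamed hips would be recorded as normal, or would fall into the subgroup without MRI signs; the documents do not support that.
- **Fatty degeneration has its own Yes/No field and is reported descriptively.** This also stands. A reader might infer that active inflammation would be overcounted, but no rule in the plan adds the items together, and the subgroup definition is left open. The defect is chiefly one of labelling.
- **Scale in this study is unknown.** A reader might apply 48.1% to the 39 planned patients. That would need the share who have MRI, the share of those with an acutely changed hip, and the overlap with effusion, and none is given. Section 3.1 says patients usually have MRI or ultrasound, not both. No patient count is projected.

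**Conclusion.** The mismatch between sections 1.1 and 4.3.7 is certain from the text. Its consequence is minor and depends on a CRF and a central reading specification that the protocol does not contain.

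If both follow the list, synovitis is not recorded as a named sign, and its change can be inferred only from effusion or from the no-lesions item. The only scale available comes from another cohort. There, synovitis is present in 96.3% of hips with acute change, and between 0 and 48.1% of those hips would have no listed active sign. This assumes that 81 is the number of hips with acute change. Those hips come from 42 patients, so they are not independent observations.

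A reader might infer a threat to the main results. There is none: the primary endpoint (BASFI) and the secondary endpoints (BASFI, BASMI, ASDAS-CRP, BASDAI, BASRI-hip) use no MRI signs. MRI may also help to confirm coxitis at screening, but section 4.3.7 does not set an eligibility rule, so no effect on eligibility is shown.

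**What to change.** Make two changes so that sections 1.1 and 4.3.7 agree:

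1. Add *Synovitis / abnormal synovial enhancement (Yes / No / not assessable)* to section 4.3.7, the CRF and the central reading.
2. Move fatty degeneration out of the active list to a separate chronic-change line, keeping its Yes/No field.

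The cost is one extra field and one relabelled line, with slightly more data entry and reading time. No imaging is added, because images are already due for central evaluation after local reading (section 6.1.2.4), so the non-interventional design is kept. Some values will be not assessable where no contrast-enhanced sequence was done or no image is available, since imaging is collected by availability. Patients with ultrasound only gain nothing. If effusion accompanies most synovitis, the gain will be small.

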2.3 Exploratory objectives

- To evaluate change of MRI signs of coxitis in AS from baseline to 12 months of therapy with golimumab in daily clinical practice
- To evaluate change of US signs of coxitis in AS from baseline to 12 months of therapy with golimumab
- To evaluate mean clinical scores (BASFI, BASMI, ASDAS-CRP, BASDAI) in subgroups of patients with or without MRI/US signs at baseline and their change at 12 months
- To evaluate occupational status of AS patients with coxitis at 12 and 24 months of therapy with golimumab in daily clinical practice

Data collected at 12 and 24 months are to be used for statistical analysis. But if these data is unavailable (e.g. due to early drop out before the final follow-up) data collected at 6 and 18 months are to be used according to analysis of last-observation-carried forward (LOCF) to minimize bias – section 8.2.1.

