For disease activity the following instruments recommended for daily clinical practice will be used: BASFI, BASMI, ASDAS-CRP. These scores will be evaluated at baseline and at 6, 12, 18, 24 months.

Radiography of hip joint is used in clinical practice. BASRI hip will be collected at baseline and at 12, 24 months.

MRI (STIR (short tau inversion recovery) sequence and fat-saturated contrast-enhanced T1-weighted sequence) and ultrasonography (US) are used in clinical practice. Usually patients have either US or MRI, but sometimes physician may administer both radiology test if one of them is unsatisfactory as a diagnostic tool. Data of these tests will be collected at baseline and at 6, 12 months.

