4.3.8 US of hip(s)

Information on hip(s) US will be collected for patients based on availability in the patient charts. If US done at screening, information on US is not be required at baseline.

Information on hip(s) US will be collected for patients based on availability in the patient charts at 6, 12 months to evaluate changes of inflammation parameters.

The following parameters of active inflammation will be determined:

- Joint effusion (expressed as Yes or No)
- Distance between lower margin of femoral neck and lower part of joint capsule expressed in millimeters
- Enthesitis at sites where ligaments and tendons are attached to bone in structures adjacent to the hip joint (expressed as Yes or No)
- Change of enthesitis from previous examination (Positive change or No change or Negative change)

At the moment, there is no standardized US scores available for hips. This is the reason for collecting information on each individual US sign of inflammation and for placing change of US signs in the Exploratory objectives.

Product: MK-8259

Protocol/Amendment No.: 021

VEAP ID NO: 6189

Date: 15-January-2018

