6.1.3.10. Hip(s) MRI

Information on hip(s) MRI (STIR (short tau inversion recovery) sequence and fat-saturated contrast-enhanced T1-weighted sequence) will be recorded at screening as one of the inclusion criterion (confirmation of coxitis) or at baseline and at 12 months.

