8.1.4 Exploratory Objectives: Calculation of Epidemiological Measures of Interest

- Change of MRI signs from baseline to 6 and 12 months of therapy (will be presented descriptively)
- Change of US signs from baseline to 6 and 12 months of therapy (will be presented descriptively)
- Mean clinical scores (BASFI, BASMI, ASDAS-CRP, BASDAI) in subgroups of patients with or without MRI/US signs at baseline and their change at 12 months
- Change of employment status of patients at 12 and 24 months of therapy (will be presented descriptively)

Product: MK-8259
Protocol/Amendment No.: 021
VEAP ID NO: 6189
Date: 15-January-2018

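### Graded MRI change and US enthesitis change are scored against the previous scan rather than baseline, so the month-12 grade of partial change has no fixed reference point

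*Combined protocol and SAP*

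**What the plan says.** The exploratory objectives in section 2.3 are anchored to baseline: "To evaluate change of MRI signs of coxitis in AS from baseline to 12 months of therapy with golimumab in daily clinical practice" and "To evaluate change of US signs of coxitis in AS from baseline to 12 months of therapy with golimumab". Section 8.1.4 keeps that anchor and adds month 6: "Change of MRI signs from baseline to 6 and 12 months of therapy (will be presented descriptively" and "Change of US signs from baseline to 6 and 12 months of therapy (will be presented descriptively".

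The graded change items use a different anchor. For MRI, section 4.3.7 lists "Change of a parameter from previous examination (Positive change or No change or Negative change"; for US, section 4.3.8 lists "Change of enthesitis from previous examination (Positive change or No change or Negative change". Neither section defines the previous examination, says what happens when month 6 is missing, or relates the grade to change from baseline.

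The other items are recorded at each examination. MRI signs are Yes/No. US effusion and enthesitis are Yes/No, and the distance from femoral neck to joint capsule is in millimetres.

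On timing, section 3.1 says of MRI and US: "Data of these tests will be collected at baseline and at 6, 12 months". Sections 4.3 and 4.3.7 and the section 5 flow chart agree. Section 6.1.3.10 instead has MRI recorded at screening "as one of the inclusion criterion (confirmation of coxitis) or at baseline and at 12 months", with no month-6 examination. Sections 4.3.7 and 4.3.8 make imaging conditional on availability, and section 3.1 requires no procedures and reports unavailable data as missing.

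**The concern.** At month 6 the previous scheduled examination is the baseline or screening one, so the grade has the reference that the objective needs. At month 12 it does so only if no month-6 scan exists. With a month-6 scan, the same field describes change over the second six months. Both situations are to be expected, because month-6 imaging depends on the chart and the sections disagree on whether month-6 MRI is collected. An unscheduled scan, which section 6 allows for, could also become the reference.

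A month-12 table of this field would then mix two quantities. It would understate improvement in patients who improved partially by month 6 and then held. Partial change is what the graded item adds to the Yes/No signs. Sections 4.3.7 and 4.3.8 both note that no standardized hip score exists, so no other severity scale covers the MRI signs or US enthesitis.

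**Working it through.** The plan gives no figure to reproduce; the check is of what the field records.

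**1. Complete appearance or disappearance of a sign.** Take one sign, Yes or No at baseline, month 6 and month 12, and compare the month-12 grade under the two references.

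| Baseline, month 6, month 12 | Against baseline | Against month 6 |
|---|---|---|
| Yes, Yes, Yes | No change | No change |
| Yes, Yes, No | Positive | Positive |
| Yes, No, Yes | No change | **Negative** |
| Yes, No, No | Positive | **No change** |
| No, Yes, Yes | Negative | **No change** |
| No, Yes, No | No change | **Positive** |
| No, No, Yes | Negative | Negative |
| No, No, No | No change | No change |

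The grades differ in 4 of 8 paths when month 6 was imaged, and in none when it was not, since the previous examination is then baseline. The errors run in both directions. In all eight paths, however, the baseline and month-12 Yes/No values give the right answer without the graded field.

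**2. Partial change while the sign stays Yes.** Suppose bone marrow edema is present at baseline, reduced at month 6 (Yes, Positive) and unchanged at month 12 (Yes, No change). Neither month-12 item shows the improvement from baseline. The same course without a month-6 scan is graded Positive at month 12.

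**3. Can the two grades be chained?** There are 3 × 3 = 9 pairs of month-6 and month-12 grades. Setting aside changes too small to grade:

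- Three pairs imply improvement from baseline: Positive–Positive, Positive–No change, No change–Positive.
- One implies no change: No change–No change.
- Three imply worsening: Negative–Negative, Negative–No change, No change–Negative.
- Two are indeterminate: Positive–Negative and Negative–Positive.

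So 3 + 1 + 3 = 7 of 9 pairs give a direction, including the example in step 2. Chaining needs both scans, and the plan states no chaining rule.

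**4. Size if the month-12 field is tabulated alone.** Let p be the share who improve without clearing by month 6 and then hold, and a the share with a month-6 scan, taken as unrelated to response. The documents give neither. The share graded Positive at month 12 is p × (1 − a), and the true share improved from baseline is p.

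| Assumed p | a = 0 | a = 0.5 | a = 1 |
|---|---|---|---|
| 30% | 30% | 15% | 0% |
| 60% | 60% | 30% | 0% |

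The shortfall is p × a. Reading the month-6 grade with the month-12 grade removes it for this course, because Positive then No change means improved.

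**The case against.** The strongest reply is that no section makes the graded item the endpoint. Sections 2.3 and 8.1.4 speak of change in signs, and sections 4.3.7 and 4.3.8 explain that each sign is collected individually because no score exists. Paired Yes/No values give presence/absence change from baseline directly, and the US distance gives a continuous change. Central reading under section 6.1.2.4 offers another route to a baseline comparison, although that section names no comparator. All of this stands, and it limits the point to partial change.

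Several stronger readings are tempting but unsupported:

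- A reader might infer that the imaging objective cannot be answered. It can be, for presence/absence and for US distance.
- A reader might infer that every early responder is recorded as unchanged. A patient whose sign clears has Yes at baseline and No at month 12 on the form. The misleading record needs partial improvement, a month-6 scan and a stable course afterwards.
- A reader might infer that the grades cannot be combined. Seven of nine pairs can be.
- A reader might take the whole US dataset to be affected. The US grade covers enthesitis alone.
- A reader might infer that an MRI will be graded against an earlier US, or the reverse. Each item sits in its own modality's section, so the natural reading is the previous scan of that modality. Section 3.1 says that patients usually have one or the other, not that they switch.

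The reply does not remove the mismatch. As defined, the item has the wrong reference at month 12 whenever a month-6 scan exists, and nothing in the plan tells the analyst how to handle it.

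**Conclusion.** The point holds in a limited form and is minor. The graded items, for any MRI parameter and for US enthesitis, do not have the reference that sections 2.3 and 8.1.4 require, and their month-12 reference varies with whether a month-6 scan exists. What is compromised is the baseline-anchored grade of partial improvement or worsening while a sign stays present. With both scans and chaining, only opposing grades remain indeterminate. If the month-12 field is tabulated alone, the understatement can be large: 60% true improvement shown as 0% to 60%. That range rests on the assumed 60% and on a tabulation that the plan does not specify.

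The imaging outcomes are exploratory and descriptive. The primary BASFI analysis, the secondary endpoints and the sample size are unaffected.

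**What to change.** In sections 4.3.7 and 4.3.8, define the grade at months 6 and 12 against the baseline (or screening) examination of the same modality and the same hip, for each sign. Change since the previous scan may stay as a separate second item. Record the grade as not assessable when no same-modality baseline image exists.

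Reconcile section 6.1.3.10 with sections 3.1, 4.3, 4.3.7, 5 and 8.1.4, so that they agree on whether month-6 MRI is collected and analyzed.

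The cost is a small change to CRF and protocol wording. No new imaging is needed, because the comparison uses the baseline or screening image where there is one. The downside is that patients without a same-modality baseline image drop out of the graded tables.
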